#### 4.2.3.3 Management of mucositis/stomatitis

General and grade specific recommendations are described in Table 4.2.3.3:1. For dose adjustment refer to [Section 4.1.4](#) and for restrictions on concomitant therapies refer to [Sections 4.2.2](#) and [Appendix 10.1](#).

Treatment is supportive and aimed at symptom control. These may include atraumatic cleansing and rinsing with non-alcoholic solutions such as normal saline, diluted salt and baking soda solution (e.g. one-half teaspoonful of salt and one teaspoon of baking soda in one quart of water every four hours); avoidance of agents containing iodine, thyme derivatives and prolonged use of hydrogen peroxide; dietary manoeuvres such as promotion of soft, non-irritating foods like ice-creams, mashed/cooked vegetables, potatoes and avoidance of spicy, acidic or irritating foods such as peppers, curries, chillies, nuts and alcohol. If the patient is unable to swallow foods or liquids, parenteral fluid and/or nutritional support may be needed. Examples of some of the agents suggested in Table 4.2.3.3:1 include: topical analgesics – viscous lidocaine 2%; mucosal coating agents - topical kaolin/pectin; oral antacids, maltodextrin, sucralfate; topical antifungals – nystatin suspension. (Adapted from [P11-09424](#))

Mouth washed with steroids (not to be swallowed) should be considered for oral ulcers as soon as they appear for CTCAE grade  $\geq 1$  until recovery at the investigator's discretion.

Table 4.2.3.3: 1 Grade specific treatment recommendations of study-drug related mucositis/stomatitis

Severity (CTCAE grading)	Description*	Treatment recommendations	Intervention concerning afatinib treatment/ dose modification
Grade 1	Minimal symptoms; normal diet	Oral rinses with agents such as non-alcoholic mouth wash with steroids (not to be swallowed), normal saline, diluted salt and baking soda solution .	No change .
Grade 2	Symptomatic, but can eat and swallow modified diet	Addition of topical analgesic mouth treatments, topical corticosteroids, antiviral therapy if herpetic infection confirmed, antifungal therapy preferably topical on a case by case basis.	Maintain dose if tolerable; Hold dose if intolerable until recovery to grade $\leq 1$ , then restart at the same dose.
Grade 3	Symptomatic and unable to adequately aliment or hydrate orally	Same as for Grade 2; institute additional symptomatic therapy (topical or systemic) as clinically indicated .	Hold dose until recovery to grade $\leq 1$ or baseline, then restart at the reduced dose according to Section 4.1.4
Grade 4	Symptoms associated with life-threatening consequences	Same as for Grade 2; institute additional symptomatic therapy (topical or systemic) as clinically indicated .	Hold dose until recovery to grade $\leq 1$ or baseline, then restart at the reduced dose according to Section 4.1.4

\* May refer to CTCAE version 4.03 for updated description of grading

#### 4.2.3.4 Management and grading of infusion reactions

The study drug infusions should always be administered in a hospital environment and under close supervision of the medically qualified staff member with immediate availability of appropriate resuscitation facilities.

Infusion reactions may occur during infusion with Xentuzumab (BI 836845) and include pyrexia, chills, rigors, dyspnoea, urticaria, bronchospasm, hypotension and hypertension. **A one hour observation period is recommended following each infusion.** Mild to moderate infusion reactions may be managed with a slower infusion rate and prophylactic antihistamines for subsequent dosing. Severe reactions require immediate and permanent discontinuation of infusion. The grading of hypersensitivity reactions will be according to the National Cancer Institute (NCI) Common Terminology Criteria for Adverse Events (CTCAE) version 4.03 ([R10-4848](#)).

Table 4.2.3.4: 1 Infusion reaction management

Infusion Reaction Grade	Management
CTCAE Grade 1 or 2	In the event of a mild to moderate CTCAE grade 1 or 2 non-allergic infusion event, the infusion rate should be reduced by 50%. Once the event has resolved the investigator should wait and deliver the infusion at the reduced rate for another 30 minutes. If tolerated, the infusion rate may then be increased to the next close rate on the patient's infusion schedule. In case of a Grade 2 event that requires therapy (e.g., antihistamines, NSAIDs, steroids, narcotics, IV fluids) or infusion interruption and resolves promptly the infusion may also be re-started at half of the infusion rate at the time of onset of the reaction.
CTCAE Grade 3	For patients experiencing CTCAE grade 3 infusion related event, infusion should be interrupted immediately and patients should receive aggressive symptomatic treatment. Only after all the symptoms have disappeared the infusion should be started. The infusion rate at restart should be half of the infusion rate at the time of onset of the reaction.
CTCAE Grade 4	Patients experiencing CTCAE grade 4 such as anaphylaxis during an infusion should have infusion immediately stopped and receive appropriate treatment including use of resuscitation medications and equipment that must be available. Such patients should be withdrawn from treatment and should be followed up.

The infusion duration may be extended to over one hour and up to a maximum of three hours, see [Section 4.1.4.1.1](#).

Proprietary confidential information.

© 2016 Boehringer Ingelheim International GmbH or one or more of its affiliated companies. All rights reserved.

This document may not - in full or in part - be passed on, reproduced, published or otherwise used without prior written permission.

The infusion reactions should be treated symptomatically as judged clinically relevant by the investigator. For symptomatic treatment of infusion reactions: hydrocortisone, antihistamines such as chlorphenamine accompanied by an antipyretic/analgesic and/or a bronchodilator is recommended.

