##### 4.2.3.1 Management of diarrhoea and hydration status

Diarrhoea occurs at a high frequency and generally begins within 2 weeks of exposure to study treatment with afatinib. Although usually mild to moderate, diarrhoea may lead to dehydration and compel treatment modification or discontinuation, so early management is essential ([Table 4.2.3.1: 1](#)). At the time of initiation of treatment with afatinib and Xentuzumab (BI 836845), patients should be given a supply of loperamide to keep with them at all times; and patients should be counselled on the appropriate use. In addition to diarrhoea management described in Table 4.2.3.1: 1, upon onset of diarrhoea CTCAE grade  $\geq 1$ , patient should take racecadotril (Tiorfan 100 mg), if available, 1 tablet twice daily (morning and evening) to be continued until recovery at the investigator's discretion.

For the use of anti-diarrhoeal medication, please refer to latest version of local drug label.

Patients must be advised to drink an adequate amount of fluids to make up for the fluid lost through diarrhoea.

Table 4.2.3.1: 1 Grade specific treatment recommendations for diarrhoea

Severity (CTCAE grade)	Description**	Intervention concerning afatinib	Specific intervention
Grade 1	
 
Increase of <4 stools per day over baseline
 
Mild increase in ostomy output compared with baseline
 
	Continue same dose	Stop laxatives and advise patient to drink at least 8-10 glasses of water or clear fluids per day; 4 mg (2 tablets) of loperamide to be taken immediately, followed by 2 mg (1 tablet) after each loose stool until bowel movements cease for 12 hours
Grade 2	
 
Increase of 4-6 stools per day over baseline
 
i.v. fluids indicated <24 hours
 
Moderate increase in ostomy output compared with baseline
 
Not interfering with activity of daily life (ADL)
 
	Continue same dose unless grade 2 diarrhoea continues for > 2 days (48 hours) in which case afatinib must be interrupted until recovered to grade $\leq 1$ followed by dose reduction	
 
Continue loperamide
 
Assess for dehydration and electrolyte imbalance
 
Consider i.v. fluids and electrolyte replacement
 

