Grade 3	
 
Increase of <math>\geq 7</math> stools per day over baseline
 
Incontinence
 
i.v. fluids <math>> 24</math> hours
 
Hospitalisation
 
Severe increase in ostomy output compared with baseline
 
Interfering with ADL
 
	Also see Section 4.1.4.3 . Dose interruption until recovered to grade $\leq 1$ followed by dose reduction*	
 
See grade 2, plus:
 
An infectious process should be ruled out with stool cultures
 
Aggressive i.v. fluid replacement <math>\geq 24</math> hours
 
Hospitalisation to monitor progress
 
Consider prophylactic antibiotics if patient is also neutropenic
 

Grade 4	
 
Life-threatening consequences (e.g. haemodynamic collapse)
 
	Dose interruption until recovered to grade $\leq 1$ followed by dose reduction*	
 
See grade 3
 

\* If despite optimal supportive care and a treatment interruption, diarrhoea does not resolve to CTCAE Grade  $\leq 1$  within 14 days, treatment with afatinib and/or Xentuzumab (BI 836845) must be permanently discontinued. In the event that the patient is deriving obvious clinical benefit according to the investigator's judgement, further treatment with afatinib and/or Xentuzumab (BI 836845) will be decided in agreement between the sponsor and the investigator.

\*\* May refer to CTCAE version 4.03 for updated description of grading

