Grade 2	Macular or papular eruptions with pruritus or other associated symptoms; localized desquamation or other lesions covering <50% of body surface area (BSA)	
 
Topical treatment as for grade 1, plus
 
short term topical steroids, e.g. prednicarbate cream 0.02%, plus
 
an oral antibiotic (for at least 2 weeks) e.g. Doxycycline 100mg b.i.d. or Minocycline hydrochloride 100mg b.i.d.
 

Grade 3	Severe, generalized erythroderma or macular, popular or vesicular eruption; desquamation covering ≥ 50% of BSA; associated with pain, disfigurement, ulceration or desquamation	
 
Topical and systemic treatment as for grade 2.
 
Consider referral to dermatologist
 
Consider systemic steroids
 
See Section 4.1.4.3 for dose modification
 

Grade 4	Generalized exfoliative, ulcerative, or bullous dermatitis	
 
See grade 3
 
Systemic steroids are recommended
 

EARLY AND LATE XEROTIC SKIN REACTIONS – PRURITUS		
Grade 1	Mild or localized	
 
Topical polidocanol cream
 
Consider oral antihistamines, e.g. diphenhydramine, dimethindene, cetirizine, levocetirizine, desloratadine, fexofenadine or clemastine)
 

Grade 2	Intense or widespread	
 
See grade 1, plus
 
oral antihistamines
 
Consider topical steroids, e.g. topical hydrocortisone
 

Grade 3	Intense or widespread and interfering with ADL	
 
See grade 2
 
See Section 4.1.4.3 for dose modification
 

XEROSIS (DRY SKIN)		
Grade 1	Asymptomatic	
 
Soap-free shower gel and/or bath oil
 
Avoid alcoholic solutions and soaps
 
Urea- or glycerine-based moisturizer
 
In inflammatory lesions consider topical steroids (e.g. hydrocortisone cream)
 

Grade 2	Symptomatic, not interfering with ADL	
 
See grade 1
 
In inflammatory lesions consider topical steroids (e.g. hydrocortisone cream)
 

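### Protocol 4.2.3.4 gives two incompatible instructions for a grade 3 infusion reaction: the text reads as stopping xentuzumab for good, the table restarts it at half rate

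*Protocol*

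**What the plan says.** The narrative of Protocol Section 4.2.3.4 sorts infusion reactions into two classes. For the lower class: "Mild to moderate infusion reactions may be managed with a slower infusion rate", with prophylactic antihistamines at later doses. For the upper class: "Severe reactions require immediate and permanent discontinuation of infusion". No CTCAE grade is attached to either class in the narrative, although the section grades hypersensitivity reactions by CTCAE version 4.03.

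Table 4.2.3.4: 1 then goes grade by grade.

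- The grade 1 or 2 row opens: "In the event of a mild to moderate CTCAE grade 1 or 2 non-allergic infusion event". It halves the rate.
- The grade 3 row interrupts the infusion and calls for aggressive symptomatic treatment. It continues: "Only after all the symptoms have disappeared the infusion should be started. The infusion rate at restart should be half of the infusion rate" that applied at onset. It is not limited to non-allergic events.
- The grade 4 row, with anaphylaxis as its example, stops the infusion and withdraws the patient from treatment.

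Three other places touch the point. Table 4.1.4.3: 1 pauses xentuzumab for a reaction of grade 3 or higher and sends the reader back to 4.2.3.4. Sections 4.1.1.1 and 4.1.4.1.1 allow the infusion to be lengthened, to at most three hours, after a reaction of grade 2 or higher.

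**The concern.** An investigator facing a grade 3 reaction finds two written instructions in one section. Under the narrative, xentuzumab is not given again. Under the table, the patient is re-exposed once symptoms clear. Both cannot be followed.

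What is at stake is patient safety and uniform handling. The trial runs at about 12 sites in four countries (Synopsis) and has no data monitoring committee (Section 3.1.1). One site could end xentuzumab while another restarts it for the same event, each able to point to the protocol. The protocol itself treats such reactions as important: exclusion criterion 11 in Section 3.3.3 bars patients who have had a severe infusion-related reaction to a monoclonal antibody.

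**Working it through.** No arithmetic applies. The documents give no rate of grade 3 infusion reactions, so no frequency is estimated. The check is a comparison of texts.

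**Step 1: set the two instructions side by side.**

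| CTCAE grade | Narrative of 4.2.3.4 | Table 4.2.3.4: 1 | Compatible? |
|---|---|---|---|
| 1 or 2 | Mild to moderate: slow the infusion, antihistamines later | Mild to moderate: halve the rate | Yes |
| 3 | Not named; falls in the severe class by elimination: stop permanently | Interrupt, treat, restart at half rate | No |
| 4 | Severe: stop permanently | Stop, withdraw from treatment | Yes |

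**Step 2: test whether grade 3 belongs in the severe class.** Within the section, the narrative has only two classes and the table assigns the lower one to grade 1 or 2. Grade 3 is left for the upper one.

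Other tables in the protocol use the words the same way. In the diarrhoea table (4.2.3.1: 1), ostomy output is described as mild at grade 1. Grade 2 reads "Moderate increase in ostomy output compared with baseline", grade 3 reads "Severe increase in ostomy output compared with baseline", and grade 4 reads "Life-threatening consequences (e.g. haemodynamic collapse". In the skin table (4.2.3.2: 2), grade 3 acneiform rash reads "Severe, generalized erythroderma or macular, popular or vesicular eruption". These are parallels in usage and do not define an infusion reaction. They support the inference without proving it.

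**Step 3: look for text that settles which rule prevails.**

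- Table 4.1.4.3: 1 pauses the drug and refers to 4.2.3.4. A pause is the first action under either rule, and the reference leads back to the section in conflict.
- The general row of that table for drug-related events of grade 3 or higher is no fallback, because its footnote 3 exempts infusion and allergic reactions.
- The permission to lengthen the infusion in 4.1.1.1 and 4.1.4.1.1 has no upper grade, which leans towards the table. It would be equally true if only grade 2 patients continued.
- The SAP contains no rule on the handling of infusion reactions.

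None of these withdraws the narrative sentence.

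**Step 4: bound the reach.**

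- Both instructions stop the infusion at once. They differ only on restart.
- Section 2.3 reports no infusion reaction in 81 patients on monotherapy. This suggests rarity but does not measure grade 3 risk with the combination.
- Section 4.1.3.2 records that the MTD/RP2D has been determined. The patients exposed to the ambiguity are therefore the 18 planned for Part B and any Part A patients still on treatment.
- The residual DLT criterion in Section 5.2.6, for other non-haematological events of grade 3 or higher, excludes infusion and allergic reactions.
- The SAP analyses response in all treated patients (Section 6.3), so a patient who stops xentuzumab stays in the denominator.

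**The case against.** The best defence is that the section never says which grade is severe. If severe means grade 4, the grade 4 row carries out the narrative sentence, the grade 3 row adds detail, and nothing conflicts. A short introduction to a graded table need not cover every grade, and a site would reasonably follow the specific row over the general sentence. The reading is possible, but it is written nowhere and leaves grade 3 outside the narrative altogether. No rule of precedence is stated, and the narrative uses the more binding verb.

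A second defence is that the sentence is aimed at allergic reactions. The grade 1 or 2 row is confined to non-allergic events, the sentence after the disputed one speaks of hypersensitivity, and the protocol elsewhere lists infusion and allergic reactions separately. However, the paragraph opens with infusion reactions in general, and neither the disputed sentence nor the grade 3 row draws the distinction. What stands is a warning about the remedy. Simply deleting the narrative sentence, or confining it to grade 4, would remove the only text in the section that could bar restart after a grade 3 allergic reaction.

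Reading discontinuation as ending only the current infusion does not help, because it is that infusion which the table restarts.

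It is also fair to say that investigators may stop treatment for an adverse event anyway (Section 3.3.4.1), so practice could still vary after a correction. That limits the benefit. It does not justify leaving two opposite instructions in place.

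**Conclusion.** The point holds: Section 4.2.3.4 is wrong as written for grade 3 reactions. It rests on one assumption, that severe includes grade 3. The two-class narrative and the grade labels in the table make this the natural reading, but it remains an inference.

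The size is small. It concerns rare events, one decision (whether to restart), and consistency between sites on a safety matter.

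A reader might infer more, and the documents do not support it:

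- *That the protocol expressly defines severe as grade 3, making this an outright contradiction.* It gives no such definition for infusion reactions.
- *That the MTD, the DLT count or the objective response result is compromised.* There is no material effect on the primary endpoints and no consequence for the SAP.
- *That the stricter rule would force linked changes across the treatment sections.* The wording in 4.1.1.1 and 4.1.4.1.1 would remain correct for grade 2, and Table 4.1.4.3: 1 only pauses and refers back.

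**What to change.** Replace the narrative sentence with one graded rule that agrees with the table, for example: *Xentuzumab is stopped at once and for good after any grade 4 reaction and after a grade 3 allergic or hypersensitivity reaction; a non-allergic grade 3 reaction is managed as in Table 4.2.3.4: 1.* Limit the grade 3 row to non-allergic events, as the grade 1 or 2 row already is, so that the two parts cannot diverge again.

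Which rule should apply at grade 3 is the sponsor's clinical decision. If permanent discontinuation is wanted for every grade 3 reaction, only the grade 3 row of Table 4.2.3.4: 1 strictly has to change.

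The cost is one sentence and one table row in a protocol amendment, communicated to sites. Data collection, sample size and SAP are untouched. Whether afatinib also stops after a grade 4 reaction is a separate question that this change does not settle.

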#### **4.2.3.5 Management of hyperglycemia**

In case of hyperglycaemia, treatment should follow standard and/or local guidelines and may include oral antidiabetics such as metformin 1g to 2.5 g/d. The appropriate expert advice should be considered in the management of hyperglycemia.

In case of a grade 3 or higher hyperglycemic event, the patient should have immediate access to consultation with an endocrinologist or specialist. When treatment with the study drug is discontinued, the need for further antidiabetic treatment has to be evaluated depending on the blood glucose levels of the patient.

### **4.3 TREATMENT COMPLIANCE**

Xentuzumab (BI 836845) will only be administered by trained staff in participating sites. Date and time of start and end of infusion, the exact amount of drug administered at each infusion will be documented in the eCRF/ study medication form.

Afatinib will be given in accordance with the protocol and the instructions of a site investigator.

The appropriate number of afatinib tablets for 4-week treatment course will be provided to patients to be self-administered at home. Patients will be asked to bring the remaining trial medication at the end of each 4-week course to the investigator site for a compliance check. The remaining film-coated tablets will be counted by the investigator/site staff and recorded at the investigator site. Discrepancies between the number of tablets remaining and the calculated number of tablets the patients should have taken must be documented and explained. At the end of each 4-week course, any remaining medication will be collected. If the patient is eligible for further treatment, a new bottle of study medication must be dispensed.

The investigator and/or the sponsor can withdraw a patient from the study in the event of serious and persistent non-compliance which jeopardizes the patient's safety or render study results for this patient unacceptable. For afatinib, a maximum of 6 consecutive doses or 7 non-consecutive doses may be missed for other reasons than drug-related AEs. Patients who miss afatinib treatment more frequently are considered non-compliant.

Afatinib should not be taken more than once a day. Patient experiencing emesis should not take a replacement dose.

## 5. VARIABLES AND THEIR ASSESSMENT

### 5.1 EFFICACY - CLINICAL PHARMACOLOGY

#### 5.1.1 Endpoints of efficacy (anti-tumour activity)

##### 5.1.1.1 Dose confirmation Part A

There are no formal efficacy endpoints for the dose confirmation part, as this is mainly concerned with the determination of the MTD/RP2D of Xentuzumab (BI 836845) in combination with afatinib. However, anti-tumour activity will also be assessed by tumour measurement and evaluation.

##### 5.1.1.2 Expansion Part B

###### Primary endpoint

The primary endpoint for Part B is the objective response (OR), defined as complete response (CR) or partial response (PR).

###### Secondary endpoints

- Disease control (DC), defined as complete response (CR), partial response (PR) or stable disease (SD).
- Time to objective response, defined as the duration of time from the date of first treatment administration until objective response.
- Duration of objective response, defined as the duration of time from first objective response to the date of first objective tumour progression or death due to any cause.

Patients with measurable and evaluable disease should have assessment according to [RECIST version 1.1](#).

#### 5.1.2 Assessment of efficacy

The assessment by the investigator and the local radiologist will be the basis for continuation or discontinuation of the trial in an individual patient (in addition to safety).

Tumour assessment will be performed every 4 weeks after start of treatment with Xentuzumab (BI 836845) and afatinib for first 8 weeks (prior to courses 2 and 3), in 8-week intervals thereafter (e.g. prior to courses 5, 7, 9, etc.) and in 12-week interval after course 16

Proprietary confidential information.

© 2016 Boehringer Ingelheim International GmbH or one or more of its affiliated companies. All rights reserved.

This document may not - in full or in part - be passed on, reproduced, published or otherwise used without prior written permission.

until PD or start of further anti-cancer treatment. Imaging may be performed within 7 days of scheduled time point. In case of tumour response (CR or PR), confirmation will be performed with a repeat assessment no less than 4 weeks after the RECIST criteria for response have been met. In the case of SD, measurement must have met the SD criteria at least once after study entry at an interval of not less than 6 weeks.

CT/MRI images not older than 30 days at start of treatment will suffice as screening images and don't have to be repeated. The EOT tumour assessment is optional if performed within the previous 4 weeks. At baseline, the investigator along with the radiologist will record the target (five target lesions maximum and maximum two per organ) and non-target lesions at baseline in the eCRF before the start of treatment. The same method of assessment and the same technique should be used to characterise each reported lesion at baseline and during follow up. Measurable lesion should be available after tumour biopsy. Lesions in previously irradiated areas may not be considered measurable at baseline unless the lesions occurred after irradiation. Response will be evaluated according to the response evaluation criteria in solid tumours (RECIST version 1.1, [R09-0262 – Appendix 10.5](#)). In the event of a delay, interruption or discontinuation of treatment, tumour assessment should continue to follow the original schedule. The schedule should be followed until progression is observed or until the patient commences further treatment for disease, whichever occurs first.

